#### 8.2.3. Pharmacokinetic Blood and BAL Samples

An assay to measure ZTI-01 concentrations in plasma, BAL, and cell pellet samples and urea in plasma and BAL samples will be conducted at a central analytical lab using a validated LC-MS/MS bioanalytical assay. Timing of samples will be with respect to the start of each dose of study drug (pre-dose and postinfusion start, when applicable). The date and time of each PK sample and BAL collection will be recorded in the eCRF. Blood PK samples will be drawn for all subjects within the following windows: -10 to -1 minute for scheduled samples at pre-dose;  $\pm 5$  minutes for scheduled samples at 30 minutes, 1 hour 15 minutes, and 2 hours; +0-5 minutes from end of infusion for the scheduled sample at 1 hour; and  $\pm 15$  minutes for scheduled samples at 5, 8, and 12 hours. BAL samples for PK (fosfomycin and urea assays) will be obtained within +/- 15 minutes of the assigned sampling time.

Instructions for collecting, processing, storage, and shipping of plasma, BAL, and urine samples will be provided in the MOP.

Blood and BAL samples are summarized in Table 7.

Study day	Dosing	Blood sampling times*	BAL sampling times §
Day 1-2 Dosing ZTI-01 6 g IV infusion over 1 hour (+10 minute window)		All subjects: Pre-dose (-10 to -1 minutes), 30 minutes (during the 1-hour infusion), and 1 hour, 1 hour 15 minutes, 2, and 5 hours after the start of the first dose	No sampling
	Second dose: ZTI-01 6 g IV infusion over 1 hour (+10 minute window)	All subjects: Pre-dose (-10 to -1 minutes)	No sampling
	Third dose: ZTI-01 6 g IV infusion over 1 hour (+10 minute window)	All subjects: Pre-dose (-10 to -1 minutes), 30 minutes (during the 1-hour infusion), and 1 hour, 1 hour 15 minutes, and 2, 5, 8, and 12 hours after the start of the third (last) infusion of ZTI-01	Each subject: Complete a single bronchoscopy with BAL at one of the five sampling times: 30 minutes (during the 1-hour infusion), 1 hour 15 minutes, 2, 5, or 8 hours from the start of the third (last) infusion of ZTI-01
Day 2 At Discharge	No further dosing	All subjects: 12 hours after the start of the third (last) infusion of ZTI-01	No sampling
* Blood PK samp	les will be drawn for all subjects	within the following windows: -10	to -1 minutes for scheduled

#### **Table 7: Pharmacokinetics sampling times**

\* Blood PK samples will be drawn for all subjects within the following windows: -10 to -1 minutes for scheduled samples at pre-dose; ±5 minutes for scheduled samples between 30 minutes, 1 hour 15 minutes, and 2 hours; +0-5 minutes from end of infusion for the scheduled sample at 1 hour; ±15 minutes for scheduled samples at 5, 8, and 12 hours. Actual times for dosing and sample will be recorded.

CONFIDENTIAL

DMID/NIAID/NIH

§ BAL samples for PK (fosfomycin and urea) will be drawn ±15 minutes for scheduled samples. Actual times for dosing and sampling will be recorded. A blood sample will be collected to measure serum urea concentration just before or during the bronchoscopy.

#### 8.2.4. Specimen Preparation, Handling, and Shipping

Please reference the protocol-specific MOP for detailed instruction for collection, processing, labeling, storing, handling and shipping.

#### 8.2.4.1. Instructions for Specimen Preparation, Handling, and Storage

All samples collected and processed for PK analysis will be shipped in accordance with the MOP to DMID-CMS at the address below, and will be tracked using DMID's Global Trace Sample Tracking system.

DMID-Clinical Materials Services (Fisher BioServices)

[name]

Germantown, MD 20876

[contact],

[contact]

Email: [contact]

Blood samples: For each blood sample timepoint (according to Sections 8.2.1 and 8.2.3), approximately 4 mL of blood will be drawn into a vacutainer tube and will be processed according to the MOP.

BAL samples: BAL samples will be collected according to Section 8.2.2 and processed for PK and urea measurements according to the MOP.

Specimen shipment: Plasma and BAL cell pellet samples will be shipped overnight on dry ice to DMID-CMS, which will then send one set of samples to the bioanalytical lab performing the PK analysis. See the MOP for details for shipping.

DMID/NIAID/NIH

# 9. ASSESSMENT OF SAFETY

## 9.1. Specification of Safety Parameters

All DMID studies are conducted in accordance with 45 CFR 46, which provides for the protection of study subjects. The Site PI or designee is responsible for the safe conduct of the trial and for reporting AEs and SAEs according to the protocol and applicable federal regulations. An Independent Safety Monitor (ISM) is a physician experienced in the conduct of clinical studies, located close to DEPRU, and appointed to independently review all SAEs and related Grade 3 AEs and thoroughly investigate those considered both serious and unexpected. The DMID Medical Monitor reviews progress and safety reports, reviews safety reports prepared in advance for SMC meetings and comments on their accuracy, reviews SMC recommendations, and has the authority to halt, suspend, or stop the study.

# 9.2. Methods and Timing for Assessing, Recording, and Analyzing Safety Parameters

#### 9.2.1. Adverse Events

ICH E6 defines an AE as any untoward medical occurrence in a patient or clinical investigation subject administered a pharmaceutical product, and that does not necessarily have a causal relationship with this treatment. An AE can therefore be any unfavorable and unintended sign (including a clinically significant laboratory abnormality), symptom, or disease temporally associated with use of the study drug, whether or not it is deemed related to the study drug. The occurrence of an AE may come to the attention of study personnel during study visits and interviews of a study subject presenting for medical care, or upon review by a study monitor. The period of observation for AE reporting will begin on Day 1 at the time of first dosing and continue through the final visit, a follow-up call on Day 3.

All AEs including local and systemic reactions not meeting the criteria for SAEs will be captured on the appropriate eCRF. Information to be collected includes event description, time of onset, clinician's assessment of severity, relationship to study drug (assessed only by those with the training and authority to make a diagnosis), outcome, action taken, and time of resolution/stabilization of the AE. All AEs occurring while on study will be documented appropriately regardless of relationship. All AEs will be followed until they adequately resolve or are determined by the PI to be medically stable (stable or improving over two assessments and no further intervention required). Any medical condition that is present at the time that the subject is screened will be considered as a baseline finding and not reported as an AE. However, if its Grade increases at any time during the trial such that it meets the AE definition specified above, it will be recorded as an AE.

All systemic and laboratory AEs will be graded using the Adverse Event Toxicity Grading Scale (Appendix B). Laboratory toxicity grading will be determined by using these tables as modified for the study to accommodate the reference range of the Central Laboratory and the acceptable ranges used in

DMID/NIAID/NIH

determining eligibility. If a subject was enrolled in the trial with a laboratory value that is outside the reference range, but within the acceptable ranges, , an AE will be recorded if it otherwise meets the definition of AE in Section 9.3 and the on-study value is higher (if initially high) or lower (if initially low) than the screening value.

#### Severity of Event:

All AEs will be assessed by the clinician using the protocol-defined grading system in Appendix B.

Changes in the severity of an AE will be documented to allow an assessment of the duration of the AE at each level of intensity to be performed. AEs characterized as intermittent require documentation of onset and duration of each episode.

#### Relationship to Study Products:

The clinician's assessment of an AE's relationship to the study drug is part of the documentation process, but it is not a factor in determining what is or is not reported in the trial. If there is any doubt as to whether a clinical observation is an AE, it will be reported. All AEs will have their relationship to the study drug assessed using the terms "related" or "not related." In a clinical trial, the study drug must always be suspect. To help assess relatedness, the following guidelines are used.

- Related: There is a reasonable possibility that the study drug caused the AE. Reasonable possibility means that there is evidence to suggest that the study drug caused the AE.
- Not Related: There is not a reasonable possibility that the study drug caused the AE.

#### 9.2.2. Serious Adverse Events

An AE or suspected AE is considered "serious" if, in the view of either the investigator or Sponsor, it results in any of the following outcomes:

- Death,
- a life-threatening AE,
- An adverse event is considered life-threatening if, in the view of either the site principal investigator or sponsor, its occurrence places the patient or subject at immediate risk of death. It does not include an adverse event that, had it occurred in a more severe form, might have caused death.
- inpatient hospitalization or prolongation of existing hospitalization,
- a persistent or significant incapacity or substantial disruption of the ability to conduct normal life functions, or
- a congenital anomaly/birth defect.

#### DMID/NIAID/NIH

#### CONFIDENTIAL

• Important medical events that may not result in death, be life-threatening, or require hospitalization may be considered serious when, based upon appropriate medical judgment they may jeopardize the subject and may require medical or surgical intervention to prevent one of the outcomes listed in this definition. Examples of such medical events include allergic bronchospasm requiring intensive treatment in an emergency room or at home, blood dyscrasias or convulsions that do not result in inpatient hospitalization, or the development of drug dependency or drug abuse.

#### All SAEs will be:

- Assessed for severity and relationship to the study drug and alternate etiology,
- Recorded on the appropriate SAE data collection form and eCRF,
- Followed through resolution,
- Reviewed and evaluated by the ISM (as deemed necessary), SMC (periodic review unless related), DMID, and IRB.

#### 9.2.3. Procedures to be Followed in the Event of Abnormal Laboratory Test Values or Abnormal Clinical Findings

A licensed study physician will make the determination of seriousness, severity, and causality, provide a medical evaluation of adverse events, and classify adverse events based upon medical judgment. Abnormal laboratory test values or abnormal clinical findings for all enrolled subjects, including values and findings noted at screening and baseline, will be assessed using the toxicity scales in Appendix B. Abnormal values and findings noted at Screening or Baseline will only be considered AEs if they increase in grade after study product administration. For abnormalities noted from the time of study drug administration, any Grade 1 or higher laboratory abnormality listed on the toxicity table in Appendix B will be entered in the database as an AE. Abnormal clinical/laboratory findings will be collected, assessed, documented, reported, and followed appropriately.

## 9.3. **Reporting Procedures**

AEs will be reported from the time of dosing on Day 1 through the Telephone Follow-up Interview on Day 3.

All AEs will be followed until resolution. Resolution of an AE is defined as the return to pretreatment status or stabilization of the condition with the expectation that it will remain chronic.

All AEs and SAEs will be reported, whether or not that are deemed causally related to the study drug. All AEs and SAEs will be recorded in the eCRF.

SAEs will be followed until resolution even if this extends beyond the study-reporting period.

CONFIDENTIAL

DMID/NIAID/NIH

The Site PI is responsible for informing the IRB of the SAE as per local requirements. DMID will be responsible of informing the US Regulatory Authority of the SAE as per federal requirements.

#### 9.3.1. Serious Adverse Events

Any AE that meets a protocol-defined serious criterion will be submitted immediately (within 24 hours of site awareness) on an SAE form to the DMID Pharmacovigilance Group, at the following address:

DMID Pharmacovigilance Group

Clinical Research Operations and Management Support (CROMS)

[name]

Bethesda, MD 20817, USA

SAE Hot Line: [name] (US) or [name] (outside US)

SAE [contact] (US) or [name] (outside US)

SAE Email Address: [contact]

In addition to the SAE form, select SAE data fields will also be entered into the DCC system (e.g., Advantage EDC). Please see the protocol-specific MOP for details regarding this procedure.

Other supporting documentation of the SAE may be requested by the DMID Pharmacovigilance Group and will be provided as soon as possible.

DEPRU will send a copy of the SAE report(s) to the ISM when they are provided to the DMID Pharmacovigilance Group. The DMID Medical Monitor and DMID Clinical Project Manager will be notified of the SAE by the DMID Pharmacovigilance Group. The DMID Medical Monitor will review and assess the SAE for regulatory reporting and potential impact on subject safety and protocol conduct.

At any time after completion of the study, if the Site PI or appropriate sub-investigator becomes aware of an SAE that is suspected to be related to the study drug, the Site PI or appropriate sub-investigator will report the SAE to the DMID Pharmacovigilance Group.

#### 9.3.2. Regulatory Reporting for Studies Conducted Under DMID-Sponsored IND

Following notification from the investigator, the IND sponsor DMID will report any suspected AE that is both serious and unexpected. DMID will report an AE as a suspected adverse reaction only if there is evidence to suggest a causal relationship between the study drug and the AE. DMID will notify FDA and all participating investigators (i.e., all investigators to whom the Sponsor is providing drug under its INDs or under any investigator's IND) in an IND safety report of potential serious risks from clinical trials or any other source, as soon as possible, but in no case later than 15 calendar days after the Sponsor determines that the information qualifies for reporting as specified in 21 CFR Part 312.32. DMID will

DMID/NIAID/NIH

also notify FDA of any unexpected fatal or life-threatening suspected AE as soon as possible but in no case later than 7 calendar days after the Sponsor's initial receipt of the information. Relevant follow-up information to an IND safety report will be submitted as soon as the information is available. Upon request from FDA, DMID will submit to FDA any additional data or information that the agency deems necessary, as soon as possible, but in no case later than 15 calendar days after receiving the request.

All SAEs designated as "not related" to the study drug will be reported to the FDA at least annually in a summary format.

## 9.3.3. Reporting of Pregnancy

Pregnancies occurring in study subjects will be reported via AdvantageEDCSM on the Pregnancy Report form. All pregnancies occurring during the trial will be followed for information regarding the course of pregnancy and any outcome, delivery and condition of the newborn. Follow-up will be provided by the investigator to the Medical Monitor (or designee) in a timely manner.

# 9.4. Type and Duration of Follow-up of Subjects after Adverse Events

All AEs will be followed until resolution or until determined by the PI to be medically stable (stable/improving and no further intervention required).

# 9.5. Halting Rules

If any of the halting rules, as outlined below, is met, further enrollment and dosing will be withheld until the SMC reviews the safety data and provides its recommendations.

- Two subjects experience any related Grade 3 systemic AE
- Two subjects experience the same related Grade 3 laboratory AE (per Medical Dictionary for Regulatory Activities High Level Group Term)
- One subject experiences a related SAE

A decision to reinitiate the trial and proceed with study drug administration will be made by DMID based on the recommendation of the SMC.

If the following individual halting rule is met, the individual will not undergo further dosing or study procedures.

• Subject experiences a grade 2 or higher abnormality in sodium, potassium, magnesium, calcium, or phosphorus, when checked approximately 2 hours prior to the bronchoscopy timepoint

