Treatment Emergent Adverse Event (TEAE)

A TEAE is defined as an AE with an onset or increase in either severity or frequency after study drug administration. Since the reporting period for AEs in this protocol is from the time of dosing on Day 1 through the Telephone Follow-up Interview on Day 3, all recorded AEs are by definition TEAEs.

Severity of Event

All AEs will be assessed by the clinician using the protocol-defined grading system.

Changes in the severity of an AE will be documented to allow an assessment of the duration of the AE at each level of intensity to be performed. AEs characterized as intermittent require documentation of onset and duration of each episode.

Relationship to Study Products:

The clinician's assessment of an AE's relationship to the study drug is part of the documentation process, but it is not a factor in determining what is or is not reported in the trial. If there is any doubt as to whether a clinical observation is an AE, it will be reported. All AEs will have their relationship to the study drug assessed using the terms "related" or "not related." In a clinical trial, the study drug must always be suspect. To help assess relatedness, the following guidelines are used.

- Related: There is a reasonable possibility that the study drug caused the AE. Reasonable possibility means that there is evidence to suggest that the study drug caused the AE.
- Not Related: There is not a reasonable possibility that the study drug caused the AE.

Serious Adverse Events (SAE)

An AE or suspected AE is considered "serious" if, in the view of either the investigator or Sponsor, it results in any of the following outcomes:

- Death,
- a life-threatening AE,
- An adverse event is considered life-threatening if, in the view of either the site principal investigator or sponsor, its occurrence places the patient or subject at immediate risk of death. It does not include an adverse event that, had it occurred in a more severe form, might have caused death.
- inpatient hospitalization or prolongation of existing hospitalization,
- a persistent or significant incapacity or substantial disruption of the ability to conduct normal life functions, or
- a congenital anomaly/birth defect.

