- Important medical events that may not result in death, be life-threatening, or require hospitalization may be considered serious when, based upon appropriate medical judgment they may jeopardize the subject and may require medical or surgical intervention to prevent one of the outcomes listed in this definition. Examples of such medical events include allergic bronchospasm requiring intensive treatment in an emergency room or at home, blood dyscrasias or convulsions that do not result in inpatient hospitalization, or the development of drug dependency or drug abuse.

All SAEs will be:

- Assessed for severity and relationship to the study drug and alternate etiology,
- Recorded on the appropriate SAE data collection form and eCRF,
- Followed through resolution,

• Reviewed and evaluated by the Independent Safety Monitor (ISM) (as deemed necessary), Safety Monitoring Committee (SMC) (periodic review unless related), DMID, and IRB.

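### An SAE judged due solely to the bronchoscopy, BAL or sedation meets no trial-level halting rule, so no automatic pause follows and only periodic SMC review is required

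*Protocol*

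**What the plan says.** Protocol 9.5 lists three trial-level triggers: two subjects with any related Grade 3 systemic AE, two subjects with the same related Grade 3 laboratory AE, and "One subject experiences a related SAE". If any is met, "further enrollment and dosing will be withheld until the SMC reviews the safety data and provides its recommendations". A separate individual rule stops dosing and procedures for one subject whose electrolytes are Grade 2 or worse about 2 hours before bronchoscopy.

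Protocol 9.2.1 (Relationship to Study Products) calls an event related when "There is a reasonable possibility that the study drug caused the AE", and adds: "In a clinical trial, the study drug must always be suspect". SAP 3.3.2 repeats the definition and explains it: "Reasonable possibility means that there is evidence to suggest that the study drug caused the AE". Neither document has a category for events related to a study procedure.

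For every SAE, the list in Protocol 9.2.2 includes "Assessed for severity and relationship to the study drug and alternate etiology" and "Reviewed and evaluated by the ISM (as deemed necessary), SMC (periodic review unless related), DMID, and IRB". SAP 3.3.2 carries the same text, including "Safety Monitoring Committee (SMC) (periodic review unless related), DMID, and IRB". SAP 6.6 provides a safety summary report for the SMC when a halting rule is met.

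Protocol 2.3.1 names respiratory distress and respiratory failure among the risks of bronchoscopy, and hypotension among the effects of any sedation given.

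**The concern.** Bronchoscopy with BAL is a research procedure here. It is done in healthy volunteers who, under Protocol 2.3.2, gain nothing directly beyond the screening laboratory tests and physical exam. The protocol itself recognises that the procedure can cause serious harm. Yet one drug-related SAE pauses the trial by rule, while after a serious harm judged purely procedural the pause depends on someone choosing to call it. What is at stake is whether more volunteers undergo the same procedure at the same site before the SMC has looked at the event.

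**Working it through.** This is a check of rule logic. The plan states no figure on the point to reproduce.

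**Step 1. Apply each trial-level trigger to an SAE judged solely procedural.** Under 9.2.1 such an event has no reasonable possibility of drug cause, so it is classed as not related.

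| Trigger in 9.5 | Needs a related event? | Met? |
|---|---|---|
| Two subjects, Grade 3 systemic AE | Yes | No |
| Two subjects, same Grade 3 laboratory AE | Yes | No |
| One subject, SAE | Yes | No |

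**Step 2. Look for another way in.** Appendix B grades every clinical event that meets the SAE criteria as Grade 3, but both Grade 3 triggers still require relatedness. The individual rule covers electrolytes before bronchoscopy and stops one subject only. Neither reaches this event. Under the current text, the chance that it causes an automatic halt is zero at any event rate.

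**Step 3. Separate what is required from what is optional.**

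- Required: report to DMID pharmacovigilance within 24 hours with a copy to the ISM, and Medical Monitor assessment of the effect on subject safety and protocol conduct (9.3.1); notice to the IRB (9.3); ISM evaluation of all SAEs (9.6.1, although 9.2.2 says only as deemed necessary); periodic SMC review (9.2.2).
- Optional: a halt by the Medical Monitor (9.1), an ad hoc SMC meeting (9.6.2), or termination by the sponsor (5.3.5).

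Nothing in the required list pauses the trial or brings the SMC in promptly.

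**Step 4. What waiting for periodic review could mean.** The Protocol Summary plans 30 completed bronchoscopies and about 12 weeks of enrollment. If they are evenly spread, 30 / 12 = 2.5 per week. Each week between the event and the review, with no discretionary halt, would mean two or three more procedures. Even spacing is an assumption, and meeting frequency is set in the SMC charter, which is not among these documents.

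**Step 5. Who would be affected by holding pending bronchoscopies.** Every BAL follows the start of Dose 3, at 0.5, 1.25, 2, 5 or 8 h, with a window of 15 minutes either way (8.2.2, 8.2.3). The longest wait from the start of Dose 3 to BAL is the nominal time plus 0.25 h: 0.75, 1.5, 2.25, 5.25 or 8.25 h. The nominal mean is (0.5 + 1.25 + 2 + 5 + 8) / 5 = 16.75 / 5 = 3.35 h. A hold on bronchoscopy adds something beyond the dosing halt only for subjects inside that interval when the halt is called.

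**The case against.** The best defence is that these rules were written to govern the study drug, and procedural risk is handled elsewhere. Section 2.3.1 provides oxygen, continuous saturation and ECG monitoring, sedation limits and direct investigator oversight. The optional powers in Step 3 could stop the trial the same day. This stands as a reason to call the gap narrow. It does not remove it, because no rule requires a pause. The SMC charter and the manual of procedures, which are not available here, could add requirements.

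A reader might infer that a procedural SAE would go without oversight. The required steps above show otherwise.

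A reader might also infer that any respiratory failure around bronchoscopy would escape the rules. That is too strong. Every bronchoscopy falls within about 8 hours of the start of Dose 3, and 2.3.1 lists dyspnea, asthma attack, anaphylaxis, tachycardia and QT prolongation among drug effects. Because 9.2.1 keeps the drug under suspicion, many serious cardiorespiratory events would be called related and would halt the trial. What remains are events clearly due to the instrument, the lavage or the sedation.

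Finally, the individual rule names study procedures and the trial-level rule names only enrollment and dosing, so a reader might infer that every trial-level halt should also hold pending bronchoscopies. The documents do not support that. 9.5 speaks of reinitiating the trial, which suggests a pause of the whole, and 5.3.2 already lets the investigator withdraw a subject on safety grounds. A hold under drug-only triggers would also have a real cost. A fully dosed subject who misses BAL is not evaluable and is replaced (5.3.4), the samples are discarded (5.3.3), and another healthy volunteer receives 18 g of drug and a bronchoscopy.

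**Conclusion.** The point holds in narrow form. By the text of 9.5, 9.2.1 and 9.2.2, an SAE judged solely procedural causes no automatic pause and requires only periodic SMC review. This is an inexpensive improvement to consider, not a fault that leaves subjects unprotected. Confidence is medium, because the SMC charter or the manual of procedures may already cover the case.

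The conclusion rests on the wording alone. It might be tempting to size the gap by putting a procedural SAE rate into the calculation behind Protocol Table 8. The documents give no such rate, nor the share of events that would be judged solely procedural, so any resulting probability would only restate its assumptions. It would also measure how often discretion replaces a rule, not how often harm follows.

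**What to change.** 1. Reword the third trigger in Protocol 9.5: *One subject experiences an SAE related to study drug or to a protocol-required procedure (bronchoscopy, BAL, sedation).*
2. Add to Protocol 9.2.1 and SAP 3.3.2 that, for SAEs, relatedness to a procedure uses the same reasonable-possibility standard and is recorded through the existing alternate-etiology entry. Without this the new trigger would have no causality definition.
3. Amend Protocol 9.2.2 and the matching text in SAP 3.3.2 so that these SAEs go promptly to the SMC. SAP 6.6 then works as written, because a halting rule is met.
4. State in 9.5 that when the procedure trigger is the one met, pending bronchoscopies are also held until SMC review. Do not impose that hold for triggers that concern the drug only.
5. Leave the two Grade 3 count triggers unchanged, so that non-serious procedural effects such as cough or sore throat do not halt the trial.

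The cost is small but not nil. No new form field, table, committee or visit is needed. A procedural SAE may bring a short pause that also stops dosing of a drug judged not to be the cause. Because 9.2.2 counts any inpatient hospitalization as serious, one admission for fever after BAL would be enough. Under this trigger, a subject already in or past Dose 3 who misses BAL becomes non-evaluable and must be replaced. As with the existing triggers, so must a subject who does not receive all three doses because of the pause.
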